9.6. Adverse Events

An Adverse Event (AE) is defined as any untoward medical occurrence in a patient whether or not related to the medical device or procedure. Adverse Events will not be captured unless they are study related or the relationship is unable to be determined.

An Adverse Device Effect (ADE) is a study-related Adverse Event. Adverse Device Effects (ADEs) that occur during the study, include AEs related to SOC, will be captured on an Adverse Event Form and reported to the Sponsor. If the relationship of the adverse event to the System is not able to be determined, it will be captured on an Adverse Event Form and reported to the Sponsor. Specific details regarding the ADE, including the event category, severity of event, and seriousness will be collected. Any necessary treatment or intervention required and the resolution status of the ADE will also be documented. ADEs will be followed to resolution. Any ADEs related to the SPRINT PNS System that meet the requirements for Medical Device Reporting (MDR) will be entered into SPR's complaint system. For SOC-related events, the sites will follow their internal policies for Medical Device Reporting (MDR).

All ADE's are further categorized as anticipated or unanticipated. Any ADE's specified in the Risk Analysis of this protocol will be considered "anticipated". All other ADE's are considered "unanticipated". Anticipated events that occur with a greater frequency than expected are also considered unanticipated.

An Unanticipated Adverse Device Effect (UADE) is defined as any serious adverse effect on health or safety or any life threatening problem or death caused by, or associated with, a device, if that effect, problem or death was not previously identified in nature, severity or degree of incidence in this protocol or application or any other unanticipated serious problem associated with a device that relates to the rights, safety or welfare of subjects.

Study Personnel will report any UADE by telephone and email to SPR Therapeutics within 24 hours of learning of the event. The event is reported by telephone and a completed AE form will be emailed to SPR Therapeutics staff as indicated in **Table 2**. Follow-up information and the complete UADE report will be forwarded to SPR Therapeutics as the event continues and/or resolves.

During training, the clinical site will be provided with detailed instructions to report ADEs and UADEs. Sponsor contact information for reports of Unanticipated Adverse Device Events is provided in **Table 2**.

Table 2: Unanticipated Adverse Device Event Sponsor Contact Information

UNANTICIPATED ADVERSE DEVICE EVENT SPONSOR CONTACT INFORMATION			
Name/Title	Email address	Telephone Number	Fax Number
[REDACTED]	[REDACTED]	[REDACTED]	[REDACTED]
[REDACTED]	[REDACTED]	[REDACTED]	[REDACTED]
[REDACTED]	[REDACTED]	[REDACTED]	[REDACTED]
[REDACTED]	[REDACTED]	[REDACTED]	[REDACTED]

It is the responsibility of the investigator to inform his/her Institutional Review Board (IRB) of any ADEs and UADEs as required by the IRB. In addition, some IRBs will require that AEs that are serious in nature, even if not study related, will be reported as well. SPR Therapeutics is responsible for furnishing the required information to the appropriate regulatory authorities.

Deficiencies related to the identity, quality, durability, reliability, usability, safety or performance of a device should be reported to SPR promptly. Sites will be provided with instructions for the reporting of device complaints in accordance with the SPR's standard operating procedures.

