4.3.1.2. Primary Safety Endpoint

The primary safety endpoint is the occurrence and type of study-related adverse events. For Group 1 (PNS), all adverse device effects (ADEs) that occur during the study will be documented. For group 2 (standard interventional management), all study-related adverse events will be documented. For both groups, AEs related to standard of care (SOC) will be collected. Specific details regarding any study-related AE will be collected on an Adverse Event Form and will be followed to resolution. The investigator will determine the severity of each event as well as its relationship to the study (i.e., device and procedure). In addition, each event will be categorized as either serious or non-serious. Any necessary treatment or intervention required and the resolution status of the event will also be documented. Study-related AEs will be tabulated and summarized at the conclusion of study. Additional details on the monitoring and adjudication of study-related AEs is described in the section regarding monitoring.

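### Section 9.6 places standard-of-care events in the ADE class and so labels known control-procedure complications unanticipated, while Section 4.3.1.2 lists them apart from the study-related events it tabulates

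*Protocol*

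**What the plan says.** Three sections of the protocol bear on this point.

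**Section 9.6 (Adverse Events).** The definition is "An Adverse Device Effect (ADE) is a study-related Adverse Event". SOC events are then brought into that class: "Adverse Device Effects (ADEs) that occur during the study, include AEs related to SOC, will be captured on an Adverse Event Form". All ADEs are sorted in two. Those "specified in the Risk Analysis of this protocol will be considered" anticipated; every other ADE is unanticipated. SOC events are treated differently in one respect only, Medical Device Reporting, where sites follow their own policies.

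**Section 4.3.1.2 (Primary Safety Endpoint).** The endpoint is the occurrence and type of study-related adverse events. The section then names three items:
- The item for the PNS arm uses the term ADE: "For Group 1 (PNS), all adverse device effects (ADEs) that occur during the study will be documented".
- The item for the control arm does not use that term: "For group 2 (standard interventional management), all study-related adverse events will be documented".
- A third item, covering both arms, is the collection of SOC-related events.

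Relationship to the study is glossed as device and procedure. The section ends by saying that study-related events will be tabulated and summarised.

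**Section 10.2 (Known and Anticipated Risks).** Group 2 receives what it would receive outside the study, so only study-specific risks are described. The visible headings cover PNS lead and stimulation risks, medial branch block and confidentiality. Much of the section is redacted.

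**The concern.** Two problems follow from reading these sections together.

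First, the sorting rule in Section 9.6 uses a reference list that Section 10.2 limits to study-specific risks. A complication that is well known for RFA, SCS or surgery would carry the label unanticipated only because of how the list was scoped. A reader of the safety report would take that label to mean that the event was not foreseen.

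Second, the primary safety endpoint counts study-related events, and the two sections disagree on whether SOC events are study-related. This matters most for Group 2, whose interventions are by design standard of care. Section 8.0 gives comparison of safety as part of the study objective, so what is counted for the control arm should not depend on which section the person preparing the tables follows.

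**Working it through.** No arithmetic applies. The check sets the sections side by side and follows one event through them: a recognised complication of an RFA, SCS or surgical procedure in a Group 2 subject. The same path applies to a Group 1 subject who also has such a procedure, which Section 5.12 allows.

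**Path A: the label**
1. Section 9.6 puts SOC-related events in the ADE class, so the complication is an ADE. The sentence is ungrammatical, but reading *include* as *including* gives the same result.
2. Section 9.6 then asks whether the event is specified in the Risk Analysis. Section 10.2 leaves out risks of usual therapies, so a complication particular to RFA, SCS or surgery is not expected to be there.
3. The default applies: the event is unanticipated.
4. The protocol's own background (Section 2.0) describes such complications. For SCS it reports complications in up to 43% of patients, and reoperation as often required. For surgery it reports risks of complications and frequent reoperation. For RFA it says less, mainly return of pain and concern about nerve destruction.

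The label given by the rule therefore conflicts with what the protocol already knows, at least for SCS and surgery. Medial branch block is an exception. It has its own heading in Section 10.2, so its events may count as anticipated, although the text beneath is redacted.

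**Path B: the endpoint**

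| Question | Section 9.6 | Section 4.3.1.2 |
|---|---|---|
| Is the complication an ADE? | Yes | Term used for Group 1 only; SOC events listed apart |
| Is it study-related? | Yes, since an ADE is by definition study-related | Suggested not, since SOC events are a separate item |
| Is it in the tabulation of study-related events? | Yes | Not stated; apparently not |

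The two columns give different Group 2 counts for the primary safety endpoint from the same data.

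**Direction and size.** Path A can only add events to the unanticipated category, and the additions come from control procedures. The number added is the count of complications particular to those procedures. The protocol gives neither event rates under this design nor the expected number of subjects per procedure, so no figure is offered. The 43% is a cited upper figure for SCS and cannot be carried over to a control arm with an unknown mix of treatments.

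**The case against.** The strongest reply is that nothing planned depends on the label. The endpoint is occurrence and type, severity and seriousness are recorded separately, and Section 8.2 says only that events are documented, reported and categorised. Section 9.6 already collects an event category, and an independent reviewer adjudicates all events under Section 9.4. This stands, and it is why the point is minor. It does not remove the wrong label, and no visible text gives the reviewer a rule for deciding whether an SOC event is study-related.

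It can also be said that Section 4.3.1.2 never states that SOC events are not ADEs, so the difference is one of terminology. That holds for what is collected, on which the two sections agree. It does not hold for what is tabulated, because the tabulation is confined to study-related events and SOC events are listed apart from them.

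Redaction limits certainty about the content of Section 10.2. The argument rests on its visible scope sentence and not on the absence of any particular heading.

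Several stronger readings are tempting, and the text does not support them:
- *SOC events may go uncaptured.* Section 9.6 says "Adverse Events will not be captured unless they are study related or the relationship is unable to be determined", which could seem to shut them out. But the same section names SOC-related events as captured on the form, and Section 4.3.1.2 says they are collected in both groups.
- *ADE counts mean different things in the two arms.* Under Section 9.6 one definition covers both. Only the unanticipated subset is distorted.
- *Serious control-device events fall under the 24-hour UADE report.* The definition reads "caused by, or associated with, a device, if that effect, problem or death was not previously identified in nature, severity or degree of incidence", and the device is not named. The study device is the more natural reading. An unanticipated ADE is not automatically a UADE: that test requires a serious event and looks to the whole protocol or application.
- *The Risk Analysis pointer leads nowhere.* That phrase is the title of Section 10.2.1 while the risks stand in Section 10.2, but both lie within Section 10.0 and a reader would find the list.

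**Conclusion.** The point holds as a minor inconsistency with two parts. Read literally, Sections 9.6 and 10.2 together class known complications particular to RFA, SCS or surgery as unanticipated ADEs. Sections 9.6 and 4.3.1.2 contradict each other on whether SOC-related events belong in the study-related tabulation that forms the primary safety endpoint. The second part matters more, because it changes what is counted for the control arm.

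The conclusion assumes that the scope sentence in Section 10.2 governs the redacted text beneath it. A reader might infer that the safety comparison is biased through the label. The protocol does not support that, since no visible passage plans a between-group comparison of anticipated and unanticipated events.

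**What to change.** Reconcile Sections 4.3.1.2, 9.6 and 10.2 with one definition:

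1. Tabulate SOC-related events in both groups as their own category, next to events related to SPRINT or to study procedures. Control-procedure events then stay visible in the safety comparison. State in Section 4.3.1.2 how this category relates to the primary safety tabulation.
2. Apply the anticipated/unanticipated split only to events related to SPRINT or to study procedures. Alternatively, keep SOC events in the split and name a reference risk list for the control procedures.
3. Keep for SOC-related events the provisions now attached to the term ADE: capture on the form, reporting to the sponsor and follow-up ("ADEs will be followed to resolution"). Simply deleting the SOC clause from Section 9.6 could lose these. If SOC events leave the ADE class, the references to ADEs in Section 5.7 (24-month discharge and follow-up), Section 5.13 (compensation) and the IRB reporting text in Section 9.6 need matching words.

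The cost is wording and possibly one added value in the event category that Section 9.6 already collects. No visit changes and no new data item is needed.

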10.0 RISK BENEFIT ANALYSIS

The potential risks and benefits to study subjects participating in this study are listed below.

10.1. Potential Benefits

Subjects in this study may not receive any direct benefit by participating in this study.

[REDACTED]

[REDACTED]

[REDACTED]

This research may benefit future patients with chronic low back pain.

[figure not shown]
[figure not shown]
10.2. Known and Anticipated Risks

The known and anticipated risks summarized below are described as expected to be either common (occurring about 10% of the time), uncommon (occurring about 1-10% of the time), or rare (occurring less than 1% of the time). Group #2 subjects will be receiving

therapies that they would normally receive if they were not participating in the study, only the risks that are specific to the study are detailed below.

[figure not shown]
[figure not shown]
The following risks apply to the subjects who receive PNS:

Risks associated with insertion of the needle introducer for lead placement

[figure not shown]
Risk of skin irritation, infection, or inflammation at the lead exit sites

Risk of the percutaneous lead breaking beneath the skin

Risk of skin irritation under the pad or bandages

Risk of discomfort or increased pain

SPR Therapeutics, Inc.
0151-CSP-000

CONFIDENTIAL
Page 48 of 62

[REDACTED]

[figure not shown]
[REDACTED]

[REDACTED]

[REDACTED]

[REDACTED]

[REDACTED]

Risks associated with medial branch block

Risk of loss of confidentiality

10.2.1. Risk Analysis

██████████ all efforts will be made to mitigate each potential risk associated with the use of the system. Despite all attempts to mitigate the risks associated with the use of the system, it is possible that these events and other unanticipated events may occur. Though subjects may experience no benefit to participating in this study, the knowledge gained from the results and the application of that knowledge toward the future development of a stimulation system may benefit future patients and significantly improve the quality of life for patients suffering from chronic low back pain. The potential risks of participation in this study have been minimized such that they are unlikely to occur and/or

have non-serious consequences. The knowledge gained from the study and the potential for relief of pain justifies the minimal potential risk.

Alternative therapies are available for the treatment of chronic low back pain. These other therapies, including pain medication for relieving pain, steroid injections to reduce pain from inflammation, acupuncture, Botox injection, or exercise and physical therapy may be beneficial and may provide pain relief or may have their own disadvantages.

11.0 STUDY ADMINISTRATION

11.1. Record Retention

By signing the Investigator Agreement, the Investigator agrees to retain study-related documents in a secure location to which access can only be gained if required. Following study completion, the following documents will be archived: the study regulatory files containing all Essential documents, including signed Informed Consent forms, patient-related materials, and CRFs. The Investigator will be required to retain all records required by this study per their contract with the sponsor. The investigator must inform SPR Therapeutics if the location of the records changes or if there are any plans to destroy the records.

11.2. Criteria for Terminating the Study

SPR Therapeutics reserves the right to terminate the study at any time. SPR Therapeutics only intends to exercise this right for valid scientific or administrative reasons, and reasons related to the protection of Human Subjects participating in this study. Principal Investigators and IRBs will be notified in writing in the event of a study termination.

11.3. Criteria for Terminating a Center

SPR Therapeutics reserves the right to suspend or stop the enrollment of subjects at a study center at any time after the study initiation if no subjects have been enrolled or if enrollment numbers are well below anticipated enrollment expectations. In addition, a study center may be terminated if the center has severe protocol violations without the necessary justification or with inadequate corrective actions.

11.4. Investigator Qualifications/Responsibilities and Investigator Training

To participate in this study, the Investigator must sign the Investigator Agreement, which documents his responsibilities in the study. The Investigator will require training on this study plan and the device. These elements will be covered during an Investigator Training session and may be conducted during the Site Initiation Visit. The Investigator/Coordinator Training will include the following elements; however, the curriculum may be slightly modified as necessary:

- Study objectives
- Subject selection criteria
- Completion of CRFs
- Device Overview and Device Operation
- Reporting of Adverse Device Effects
- Good Clinical Practice Regulations

- Any other information that is deemed necessary to ensure that the clinical team is knowledgeable about the protocol, the Device, and the manner in which it will be used in this study.
- Device/lead placement training will also occur prior to the first lead placement.

11.5. Statements of Compliance

11.5.1. Declaration of Helsinki

This research study shall be conducted in accordance with the ethical principles that have their origin in the Declaration of Helsinki.

11.5.2. International and National Standards

This research study shall comply with any applicable federal (21 CRF Parts 11, 50, 56, 812) and international standards (ISO 14155) and ICH Good Clinical Practice Guidelines.

11.5.3. Institutional Review Boards

This research study shall not begin until the applicable approvals have been obtained from the governing Institutional Review Board (IRB) where the research will be conducted. Any additional requirements imposed by the governing regulatory authorities and/or IRB will be followed.

12.0 DEVIATIONS TO THE PROTOCOL

Protocol deviations are defined as an unplanned excursion from the protocol that is not implemented or intended as a systematic change, or any other unplanned instance(s) of protocol noncompliance.

The Investigator must not deviate from the protocol, except when necessary to protect the life or physical well-being of the subject. Whenever possible, the Investigator will obtain the permission in advance for protocol violations from SPR Therapeutics and the governing IRB (in accordance with its reporting requirements). Deviations will be recorded on a protocol deviation log and reviewed by the study monitor to address any needs for corrective and preventive action. Deviations will also be reported as part of the final study report.

13.0

[figure not shown]
14.0

A high-contrast, black and white image featuring a series of horizontal white bars of varying lengths. These bars are arranged in a staggered, non-linear pattern, creating a sense of depth or a stylized data visualization. The bars are set against a solid black background, which provides a stark contrast. The lengths of the bars vary, with some being relatively short and others being significantly longer, though all appear to be of equal width. The overall effect is minimalist and abstract, resembling a barcode or a series of data points.

SPR Therapeutics, Inc.
0151-CSP-000

CONFIDENTIAL
Page 56 of 62

Appendix C. Subject Participation Flow Chart for Visits 1-18*
